8.0 SAFETY ANALYSES

The numbers and percentages of subjects with any subdural hematomas and any parenchymal hematomas will be presented by treatment and visit (Days 8, 28, 168, and 336) and by treatment across all visits. Dose response analyses of these two variables will be performed using a logistic regression model with a term for dose as a continuous variable, with the control dose excluded from the analyses. For each treatment, the total numbers of subdural hematomas and parenchymal hematomas across all visits will be presented. Subdural hematoma and parenchymal hematoma volume and status will be summarized by visit using counts and percentages.

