4.0 DESCRIPTION AND JUSTIFICATION OF TREATMENT REGIMEN

4.1 Dosages

All dosages of cells are to be administered stereotactically through one burr-hole craniostomy using 3 needle tracks within and adjacent to the focal area of injured brain tissue using 5 cell deposits per track at varying depths, with 20 μ L per deposit. Concentrations of cell suspensions to be used will vary depending on the total dosage required per patient. See Table 2 below.

Total SB623 Cells/Pt.	Total SB623 Cells/Deposit	Total SB623 Cells/Track	Concentration of SB623 Cells	Total Volume per Deposit, per Track, and Total
2.5×10^6	1.7 X 10 ⁵	8.3 X 10 ⁵	8.3 X 10 ⁶ cells/mL	20 μL, 100 μL, and 300 μL
5.0 X 10 ⁶	3.3 X 10 ⁵	16.5 X 10 ⁵	17 X 10 ⁶ cells/mL	20 μL, 100 μL, and 300 μL
10 X 10 ⁶	6.6 X 10 ⁵	33 X 10 ⁵	33 X 10 ⁶ cells/mL	20 μL, 100 μL, and 300 μL

Table 2Dosages, Volumes and Cell Concentrations

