12.0 SAFETY ANALYSES

12.1 Adverse Events

All safety analyses will be performed on the safety population.

The summary of AEs will be limited to treatment emergent AEs, which are defined as any adverse event with onset on or after the initiation of treatment or any adverse event already present that worsens in intensity following exposure to study treatment.

The number and percentage of subjects with at least one adverse event, at least one serious adverse event (SAE), and at least one adverse event that led to discontinuation from the study will be presented. The number and percentage of subjects having an adverse event in each System Organ Class (SOC) and having each individual type of adverse event (Preferred Term) will be presented. Fisher's Exact Test will be used to test for differences between treatments (pooled SB623 vs. sham surgery) in the proportion of subjects experiencing AEs in each SOC. This analysis will also be performed for SAEs, except that no statistical testing will be performed. Adverse events will also be summarized at the event level by SOC/Preferred Term and severity, by SOC/Preferred Term and relationship to study product, by SOC/Preferred Term and relationship to surgery, and by SOC/Preferred Term and action taken.

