8.0 SAFETY ANALYSES

The summary of SAEs will be limited to treatment emergent SAEs, which are defined as any serious adverse event with onset on or after the initiation of treatment or any adverse event already present that worsens in intensity following exposure to study treatment.

For each treatment group (control patients, pooled SB623 patients, and each SB623 dose group) and each category of each genotyping subgroup variable, the following results will be presented: number and percentage of subjects with at least one SAE and descriptive statistics for the number of SAEs per patient. For each category of each genotyping subgroup variable, a two-sided Fisher's Exact Test will be used to test for a difference between treatments (pooled SB623 versus control) in the proportion of patients with at least one SAE. For each treatment group, a two-sided Fisher's Exact Test will be used to test for a difference among categories of the subgroup variables in the proportion of patients with at least one SAE.

For each genotyping subgroup variable, a logistic regression analysis of SAE incidence will be performed. The model will include terms for the genotyping subgroup variable, treatment (pooled SB623 or control), and the genotyping subgroup variable by treatment interaction. The p-value for each term in the model will be presented. A statistically significant interaction term would indicate that the effect of treatment on SAE occurrence is different among the categories of the genotyping subgroup variable.

For each genotyping subgroup variable, a dose response analysis of the incidence of SAEs will be performed using a logistic regression model with terms for the genotyping subgroup variable, SB623 dose (as a continuous variable), and the genotyping subgroup variable by SB623 dose interaction. The control group will be excluded from these analyses. The p-value for each term in the model will be presented. A statistically significant interaction term would indicate that the effect of dose on SAE occurrence is different among the categories of the genotyping subgroup variable.

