5.0 STATISTICAL CONSIDERATIONS

5.1 General Methodology

The statistical analysis of the data will be performed using SAS[®] version 9.4 or higher. All statistical tests will be performed at the 0.05 significance level.

The head MRI variables will be documented using summary tables and subject data listings. Continuous variables will be summarized using descriptive statistics, specifically the number of observations, mean, median, standard deviation, minimum and maximum. Categorical variables will be summarized by frequencies and percentages. For the most part results will be presented for the four treatment groups separately and the three SB623 dose groups pooled. The three SB623 dose groups will be pooled for all statistical tests comparing SB623 to sham surgery, except where noted otherwise (e.g., dose response analyses).

Data listings will be sorted by treatment group and subject ID. All date fields will be presented in a format of ddmmyyyy (i.e., 01Jan2018) in the listings.

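### No pooled SB623-minus-sham risk difference or confidence interval is planned for intracranial hematoma or for treatment-emergent SAEs, and the one hematoma-specific test leaves sham out

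*SAP*

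**What the plan says.** **Hematoma (SAP Appendix E, 8.0).** "The numbers and percentages of subjects with any subdural hematomas and any parenchymal hematomas will be presented by treatment and visit", and also across all visits. Total counts, volume and status are summarised. Section 5.1 of that appendix says that, for the most part, "results will be presented for the four treatment groups separately and the three SB623 dose groups pooled". The inferential step is a logistic model "with a term for dose as a continuous variable, with the control dose excluded from the analyses". No difference, interval or test against sham is described.

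**Overall AEs and SAEs (SAP Appendix A, 12.1).** For all treatment-emergent AEs, Fisher's exact test is used to "test for differences between treatments (pooled SB623 vs. sham surgery) in the proportion of subjects experiencing AEs in each SOC". For serious events: "This analysis will also be performed for SAEs, except that no statistical testing will be performed".

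**SAEs in the supplements (SAP Appendix C, 8.0; Appendix D, 9.0).** Within each genotype and antibody category, Fisher's test is used to "test for a difference between treatments (pooled SB623 versus control) in the proportion of patients with at least one SAE". Each supplement also fits a logistic model of SAE incidence with subgroup, treatment and their interaction, and presents a p-value for every term. No odds ratio or interval is mentioned.

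**The procedure (Protocol 4.1 and 6.0).** "All dosages of cells are to be administered stereotactically through one burr-hole craniostomy using 3 needle tracks". Table 2 gives 5 deposits per track, 20 µL per deposit and 300 µL in total at every dose; only the cell concentration changes. Sham surgery stops at the outer table of the skull and leaves the inner table and dura intact.

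**The concern.** Bleeding from opening the dura and passing needles through brain is a risk of the implant procedure that sham patients do not carry. The design randomises against sham and so can estimate this excess risk, yet the hematoma model discards the sham arm. A reader who finds one hematoma p-value in the report, and finds it non-significant, could take it as evidence about bleeding in general, when it concerns only differences between doses.

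For SAEs, p-values against sham appear in the subgroup supplements, where the samples are split, while the whole-trial comparison has no measure of uncertainty. This sits oddly with the rest of the plan. Laboratory tests and vital signs (SAP 12.2, 12.3) and every head MRI variable (Appendix E, 7.2) get a pooled SB623-minus-sham difference in mean change with a two-sample t-test.

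**Working it through.** **1. Arm sizes, from the plan's own calculation (SAP Appendix A, 3.4).** Inputs: difference 10.0 − 3.0 = 7.0, SD 7.25, two-sided alpha 0.05, power 80%, 3:1.

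Sham n = (1 + 1/3) × (1.960 + 0.842)² × (7.25/7.0)² = 1.333 × 7.849 × 1.073 = 11.2, rounded up to 12. The total is 48 (36 + 12), as stated; exact t-test power at 36/12 is 80.9%. Then 48 × 1.08 = 51.8, about 52, also as stated. At 3:1 this is 39 SB623 and 13 sham, or 13 per dose.

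**2. What the dose slope can detect.** The model is logit P(hematoma) = b0 + b1 × dose, fitted to SB623 patients only. Risk from penetration is common to all doses and sits in b0. With sham excluded, nothing is left to compare b0 with; b1 = 0 is compatible with any excess over sham.

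Exact enumeration with 13 patients at each of 2.5, 5 and 10 million cells and the same assumed risk at every dose gives these rejection rates for b1 = 0:

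| Common risk | 5% | 10% | 20% | 30% | 40% | 50% |
|---|---|---|---|---|---|---|
| Wald test | 0.1% | 0.6% | 2.5% | 3.8% | 4.2% | 4.4% |
| Likelihood ratio test | 8.2% | 9.1% | 6.0% | 5.5% | 5.6% | 5.6% |

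These are false-positive rates for a dose effect and do not depend on the sham rate.

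**3. What the missing contrast would show.** Event counts are assumed. The Newcombe interval takes Wilson limits (l, u) for each proportion: lower = d − √[(p1 − l1)² + (u0 − p0)²], upper = d + √[(u1 − p1)² + (p0 − l0)²], where d = p1 − p0.

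For 12/39 v 0/13: p1 = 0.308 (Wilson 0.186 to 0.464), p0 = 0 (Wilson 0 to 0.228).
- Lower: 0.308 − √(0.122² + 0.228²) = 0.049.
- Upper: 0.308 + 0.157 = 0.464 (unrounded inputs).

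| SB623 | Sham | Difference (points) | 95% CI | Fisher p |
|---|---|---|---|---|
| 4/39 | 0/13 | +10.3 | −13.4 to +23.6 | 0.56 |
| 8/39 | 0/13 | +20.5 | −4.3 to +35.5 | 0.18 |
| 12/39 | 0/13 | +30.8 | +4.9 to +46.4 | 0.024 |
| 12/39 | 2/13 | +15.4 | −14.1 to +34.5 | 0.47 |

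For sham alone, the exact upper limit for 0/13 is 1 − 0.025^(1/13) = 24.7%.

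**4. Why a p-value alone is not the answer.** Exact power of Fisher's test at 39 v 13:

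| SB623 risk | 10% | 20% | 30% | 40% | 50% |
|---|---|---|---|---|---|
| Sham 0% | 0.1% | 14.1% | 65.5% | 95.5% | 99.8% |
| Sham 5% | 0.3% | 7.4% | 39.4% | 72.5% | 90.2% |

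With 0/13 in sham, at least 11/39 is needed for p < 0.05 (p = 0.047; 10/39 gives 0.0502). At low or moderate rates the test would usually be non-significant even with a real excess.

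**The case against.** The other side has several good points.

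- Hematoma percentages are presented for sham, and by Appendix E 5.1 generally for each dose and pooled SB623, so the crude difference is visible. A reader might infer that the plan gives no estimate at all; it does not go that far. What is absent is a stated contrast and its interval.
- A reader might infer that SAEs are compared with sham only inside subgroup categories. The logistic models in Appendices C and D use all categories together and report a treatment-term p-value. It is a poor overall test, since the interaction makes it depend on how the terms are coded and no effect size is given, but it exists.
- Hematomas and SAEs recorded as AEs also enter the SOC-level Fisher tests in SAP 12.1, mixed with other terms.
- The safety objective (Protocol 5.1.2) is to evaluate safety and tolerability and names no comparator. Protocol 18.3 plans AE and SAE reporting as numbers and percentages, so descriptive SAE reporting is consistent with the protocol.
- Ranking hematoma as the leading harm is a judgement; Protocol 14.0 lists intracranial infection, bleeding and seizures together.
- The only bleeding rate cited (Protocol 2.3.3) is 0.36% needing craniotomy for hematoma evacuation in general stereotactic surgery, a narrower event. At low rates a sham comparison has almost no power.
- The table shells are not in the available text, so an extra row there cannot be excluded.

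All of this stands and narrows the point. None of it supplies a hematoma-specific comparison with sham, or an interval for hematoma or SAEs. Low power favours an interval, which shows how much excess risk remains possible.

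**Conclusion.** The point holds in a limited form. The methods text plans no pooled SB623-minus-sham risk difference or confidence interval for hematoma or for any treatment-emergent SAE. The one hematoma-specific test cannot show bleeding due to penetration: when risk is equal across doses it rejects in about 0 to 4% (Wald) or 6 to 9% (likelihood ratio) of trials, whatever the excess over sham.

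The documents do not support a claim that safety is uncompared with sham throughout, or that a large harm would go unseen, since the percentages by arm are reported. The loss is in quantified uncertainty. It matters because 13 sham patients leave much open: zero sham events is still compatible with a sham risk of up to about 25%.

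This rests on 39 v 13 patients, on event rates assumed over 5 to 50%, and on bleeding from penetration not depending on cell concentration. If concentration does affect bleeding, the dose slope has some value as a secondary analysis.

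**What to change.** **SAP Appendix E, 8.0.** Make the main comparison the pooled SB623-minus-sham risk difference with a 95% CI (Newcombe or Miettinen-Nurminen), separately for patients with any subdural and any parenchymal hematoma across visits, in the Safety population. Keep the dose slope as secondary. State which scans count as across visits: the by-visit list has Days 8, 28, 168 and 336, but section 3.1 also schedules a Day 2 MRI.

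**SAP Appendix A, 12.1.** Add the same risk difference and interval for patients with at least one treatment-emergent SAE, shown ahead of the subgroup SAE tests. Leave the no-testing rule for SAEs by SOC in place: removing it would switch on a series of SOC-by-SOC tests with no multiplicity control and few sham patients.

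A Fisher p-value is optional support. At the margin it can disagree with the interval: 10/39 v 0/13 gives p = 0.0502 with a Newcombe interval of +0.3 to +41.1 points.

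The cost is a few sentences and table rows, with no new data. The intervals will be wide and should be read that way. The SAP addendum records analyses added after the interim unblinding, so anything added after that should be labelled post hoc.

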1.0 INTRODUCTION

This document details the analysis plan for the analysis of leg activity monitoring variables for the study entitled “A Double-Blind, Controlled Phase 2 Study of the Safety and Efficacy of Modified Stem Cells (SB623) in Patients with Chronic Motor Deficit from Traumatic Brain Injury (TBI)”. It describes the proposed efficacy analyses, including planned summary tables and by-subject data listings. This document is a supplement to the main statistical analysis plan (SAP).

2.0 OBJECTIVES

The overall objective of the study is to evaluate the safety and efficacy of SB623 cells stereotactically implanted in the brains of patients with TBI.

The objective of the leg activity monitoring analyses is to evaluate the efficacy of intracranial administration of SB623 cells with respect to leg activity monitoring variables.

3.0 STUDY DESIGN

3.1 Overview

This is a double-blind, sham surgery controlled study of stereotactic, intracranial injection of SB623 cells in patients with fixed motor deficits from TBI. The study will be conducted at approximately 30 sites in North America (i.e., United States), Eastern Europe (i.e., Ukraine), and Asia Pacific (i.e., Japan).

Table 1 in the main SAP lists the procedures to be followed throughout the course of the study. Activity data will be downloaded at the clinical site and changes from Baseline in activity parameters will be calculated at Days 28, 84, 168, 252, and 336.

3.2 Method of Assigning Subjects to Treatment

Two groups, Group 1 and Group 2, will receive SB623 and sham surgery, respectively, in a 3:1 randomization scheme. Group 1 will be further randomized in a 1:1:1 ratio to receive either 2.5 million, 5 million, or 10 million SB623 cells. Randomization will be performed via an interactive web/voice response system (IXRS). For subjects enrolled outside of Japan, the randomization will be stratified by Glasgow Outcome Scale-Extended (GOS-E) score (i.e., scores 3, 4, 5 or 6); for subjects in Japan, the randomization will not be stratified.

3.3 Blinding

This is a double-blind study. The blind will be maintained by strict role definition and procedures as described in the protocol.

3.4 Changes to the Protocol-Specified Analyses

No changes were made to the protocol-specified analyses.

4.0 EFFICACY ENDPOINTS IN THIS STATISTICAL ANALYSIS PLAN

The efficacy endpoints of interest in this SAP are variables from the leg activity monitoring.

5.0 STATISTICAL CONSIDERATIONS

5.1 General Methodology

The statistical analysis of the data will be performed using SAS[®] version 9.4 or higher. All statistical tests will be performed at the 0.05 significance level.

Leg activity monitoring variables will be documented using summary tables, subject data listings, and summary figures. Continuous variables will be summarized using descriptive statistics, specifically the number of observations, mean, median, standard deviation, minimum and maximum. Categorical variables will be summarized by frequencies and percentages. For the most part results will be presented for the four treatment groups separately and the three SB623 dose groups pooled. The three SB623 dose groups will be pooled for all statistical tests comparing SB623 to sham surgery, except where noted otherwise (i.e., dose response analyses).

Data listings will be sorted by treatment group and subject ID. All date fields will be presented in a format of ddmmyyyy (i.e., 01Jan2018) in the listings.

5.2 Adjustments for Covariates

No adjustments for covariates will be made.

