3.0 STUDY DESIGN

3.1 Overview

This is a double-blind, sham surgery controlled study of stereotactic, intracranial injection of SB623 cells in patients with fixed motor deficits from TBI. The study will be conducted at approximately 30 sites in North America (i.e., United States), Eastern Europe (i.e., Ukraine), and Asia Pacific (i.e., Japan).

Table 1 in the main SAP lists the procedures to be followed throughout the course of the study. Head MRIs will be obtained at Screening, Baseline, and Days 2, 8, 28, 168, and 336. DTI and DSC imaging will be obtained at Baseline, and Days 28, 168, and 336.

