7.2 Other Efficacy Endpoints

For the pooled SB623 versus sham surgery treatment groups, descriptive statistics will be presented by visit for the actual values and the changes from baseline for each head MRI variable. The difference between treatment groups (pooled SB623 - sham surgery) in the mean change from baseline will also be presented. For each head MRI variable, the one-sample t-test will be used to test whether the mean change from baseline equals 0 for each post-baseline time point. The two-sample t-test will be used to test whether the mean changes from baseline are equal for the two treatments (pooled SB623 vs. sham surgery). Analyses will be performed overall and for the head MRI subgroups specified in Section 5.6.

In addition, each head MRI variable will be analyzed to examine dose response. For each head MRI variable and treatment group (2.5 million SB623 cells, 5 million SB623 cells, 10 million SB623 cells, pooled SB623, and control), the one-sample t-test will be used to test whether the mean change from baseline equals 0 for each post-baseline time point. Linear regression analyses with a term for dose will be used to test the null hypothesis that the coefficient of dose equals 0. Dose will be a continuous variable with the control treatment assigned a value of 0. The p-value from the test of the null hypothesis that the coefficient of dose equals 0 will be presented. Analyses will be performed overall and for the head MRI subgroups specified in Section 5.6.

The numbers and percentages of subjects with FLAIR lesion at Day 8 and with enhancing lesion at Day 8 will be presented by treatment group. Descriptive statistics will be presented for maximum diameter of FLAIR lesion at Day 8, and the x, y, and z dimensions of FLAIR lesion at Day 8. The number and percentage of subjects will be presented for each FLAIR lesion location at Day 8.

The actual values and changes from baseline will be summarized by visit and presence of FLAIR lesion at Day 8 subgroup for the FMMS score using descriptive statistics.

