7.0 EFFICACY ANALYSES

In this SAP, the following variables from Leg Activity Monitoring will be analyzed.

- Average Daily Total Energy Expenditure (affected side and non-affected side separately)
- Average Daily Activity Counts (affected side and non-affected side separately)
- Average Non-Sedentary Time per Day (affected side)
- Average Time of Moderate or Vigorous Activity per Day (affected side)

For the first two endpoints listed above, the value of the endpoint will be calculated as follows. The mean of each day's value will be calculated for the two-week period prior to Baseline, which will be the baseline value for this endpoint, and for the two-week period prior to each study visit.

Average Non-Sedentary Time per Day: The leg activity monitor can measure the time in minutes within each activity range. Activity range is categorized as sedentary, light, moderate, or vigorous based on energy expenditure. The light, moderate, and vigorous activity ranges are considered non-sedentary. The mean of each day's time within the non-sedentary range will then be obtained for the two-week period prior to Baseline, which will be the baseline value for this endpoint, and for the two-week period prior to each study visit.

Average Time of Moderate or Vigorous Activity per Day: The leg activity monitor can measure the total amount of time in minutes within the moderate or vigorous activity ranges throughout each day. The mean of each day's value will then be calculated for the two-week period prior to Baseline, which will be the baseline value for this endpoint, and for the two-week period prior to each study visit.

For the pooled SB623 and sham surgery treatment groups, descriptive statistics will be presented by visit for the actual values and the changes from baseline for each leg activity monitoring variable. The difference between treatment groups (pooled SB623 - sham surgery) in the mean change from baseline will also be presented. For each leg activity monitoring variable, the one-sample t-test will be used to test whether the mean change from baseline equals 0 for each post-baseline time point for each treatment group. Two-sided, two-sample t-tests will be used to test whether the mean changes from baseline are equal for the two treatments (pooled SB623 vs. sham surgery). Analyses will be performed overall and for the subgroups specified in Section 5.6.

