In addition, each leg activity monitoring variable will be analyzed to examine dose response. For each leg activity monitoring variable and SB623 dose group (2.5 million SB623 cells, 5 million SB623 cells, 10 million SB623 cells), a two-sided, one-sample t-test will be used to test whether the mean change from baseline equals 0 for each post-baseline time point. Linear regression analyses with a term for dose will be used to test the null hypothesis that the coefficient of dose equals 0. Dose will be treated as a continuous variable, and the control treatment will not be included in this analysis. The p-value for the test of the null hypothesis that the coefficient of SB623 dose equals 0 will be presented.

Analyses will be performed overall and for the subgroup specified in Section 5.6.

Graphs will be presented summarizing the mean change from baseline in the Average Daily Activity Count (affected side and non-affected side separately) over time by treatment group (pooled SB623 and control) for both the mITT and Per Protocol populations. The graphs will plot

the mean changes (\pm standard error) over time, as well as the p-value at each timepoint from a two-sided, two-sample t-test testing the null hypothesis that the true mean change is equal for the two treatments.

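### Leg-activity and head-MRI changes are compared only without baseline adjustment, although baselines are collected: a low-priority case for adding ANCOVA beside the planned tests

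*SAP*

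**What the plan says.** **Leg activity (SAP Appendix F).** Section 5.2 reads in full: "No adjustments for covariates will be made". Section 7.0 compares pooled SB623 with sham at each visit: "Two-sided, two-sample t-tests will be used to test whether the mean changes from baseline are equal for the two treatments". For dose response: "Linear regression analyses with a term for dose will be used to test the null hypothesis that the coefficient of dose equals 0", and "Dose will be treated as a continuous variable, and the control treatment will not be included in this analysis". The baseline is defined in the same section as a daily mean over the "two-week period prior to Baseline, which will be the baseline value for this endpoint".

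**Head MRI (SAP Appendix E).** Section 7.2 plans: "The two-sample t-test will be used to test whether the mean changes from baseline are equal for the two treatments". The dose regression again has dose as its only term, but here "Dose will be a continuous variable with the control treatment assigned a value of 0". Baseline values exist: section 3.1 schedules a head MRI at Baseline and adds that "DTI and DSC imaging will be obtained at Baseline, and Days 28, 168, and 336". The covariate section of this appendix (5.2) adjusts the Fugl-Meyer endpoint only, not the imaging variables.

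**Elsewhere.** SAP Appendix A, 5.2 adjusts the continuous clinical change endpoints for their own baseline and for GOS-E. Appendix A, 10.4 prints unadjusted t-test p-values on graphs of those endpoints, but an adjusted model is reported beside them. Appendix A, 12.2 and 12.3 compare laboratory and vital-sign changes by unadjusted two-sample t-test, with no adjusted model. No section adds a baseline-adjusted arm or dose comparison for leg activity or head MRI, and none says why it is left out.

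**The concern.** A t-test on change fixes the baseline coefficient at 1, whereas ANCOVA estimates it. When follow-up is imperfectly correlated with baseline, the change score over-corrects. It then usually has a larger variance, and any chance difference in baseline means passes into the estimated effect through regression to the mean.

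The sham arm is small, about 13 of 52. It will probably be smaller still for leg activity: Protocol 15.10 makes monitoring mandatory only in the US and Japan, and the listed endpoint (Protocol 5.2.3; SAP Appendix A, 4.3, item 12) is confined to lower extremity deficit patients. An uncorrected imbalance could create or hide an apparent signal in variables that are tested at 0.05 without multiplicity control. What is at stake is sensitivity and readability of exploratory results. The primary Fugl-Meyer comparison is not involved.

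**Working it through.** **The plan's own sample size.** SAP Appendix A, 3.4 sizes only the Fugl-Meyer endpoint: difference 10.0 − 3.0 = 7.0, SD 7.25, two-sided alpha 0.05, 80% power, 3:1. Noncentral-t power is 80.9% at 36:12 and 77.3% at 33:11, so 48 reproduces. 48 × 1.08 = 51.8 gives the stated 52, which is 39:13. No size or power is stated for leg activity or MRI.

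**Assumed inputs, not in the documents.** Correlation r between baseline and follow-up of 0.5, 0.7 or 0.9 (stable deficits and two-week means make the upper end plausible); a leg-activity size of N=30 (22:8); smaller sizes for subsets; at first, equal variances and equal baseline slopes in the two arms.

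**Precision.** With common variance s², change has variance 2s²(1−r) and the ANCOVA residual s²(1−r²). The ratio is (1+r)/2, times (N−3)/(N−4) for estimating the slope.

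| N | r=0.9 | r=0.7 | r=0.5 | break-even r = 1−2/(N−3) |
|---|---|---|---|---|
| 52 | 0.970 | 0.868 | 0.766 | 0.96 |
| 30 | 0.987 | 0.883 | 0.779 | 0.93 |
| 24 | 0.997 | 0.892 | 0.787 | 0.90 |
| 16 | 1.029 | 0.921 | 0.812 | 0.85 |

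So variance falls by about 3%, 13% and 23% at N=52, and by 1%, 12% and 22% at N=30. Simulation agrees at 39:13 and 22:8. Where the t-test has 80% power, ANCOVA has about 81%, 85% and 89% at N=52, and 80%, 85% and 89% at N=30.

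**Chance imbalance.** At 39:13 the SD of the difference in baseline means is √(1/39+1/13) = 0.320 SD, so P(difference > 0.5 SD in either direction) = 0.118. At 22:8 the figures are 0.413 and 0.226. A 0.5 SD imbalance moves the change-score difference by 0.5(1−r), against a standard error of √(2(1−r)) × 0.320. At 39:13 this is 0.35, 0.60 or 0.78 standard errors at r = 0.9, 0.7 or 0.5.

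**Dose slope (simulated variance ratios at r = 0.9, 0.7, 0.5).** Appendix E set, doses 0/2.5/5/10 with 13 each: 0.973, 0.863, 0.765. Appendix F set, 2.5/5/10 with 13 each: 0.979, 0.875, 0.769; with 7/7/8: 1.004, 0.894, 0.790.

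**Unequal variances (N=52).** With follow-up SD k times baseline SD, the ratio is k²(1−r²)/(1+k²−2rk) × 49/48. For k=1.2 it is 0.997, 0.986, 0.889 at r = 0.9, 0.7, 0.5; for k=0.8 it is 0.621, 0.641, 0.583.

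**Unequal slopes (39:13, equal SDs, sham r=0.95, SB623 r=0.7).**
- Pooled slope: (12×0.95 + 38×0.7)/50 = 0.76.
- An arm's variance at slope b is 1+b²−2br. At b=0.76: sham 0.1336, SB623 0.5136, giving 0.1336/13 + 0.5136/39 = 0.02345.
- At b=1 (change score): sham 0.10, SB623 0.60, giving 0.10/13 + 0.60/39 = 0.02308.
- Estimating the slope adds about 0.0009, so the ratio is about 0.0243/0.0231 = 1.05. Simulation gives 1.05 to 1.06.

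With sham r=0.95 and SB623 r=0.8, variance is about 3% higher at 39:13; with 0.9 and 0.7 there is no material difference.

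**The case against.** The strongest reply is that this is a preference between two valid analyses, with little to gain where these data probably lie. At r=0.9 the gain is 3% at N=52, 1% at N=30 and nil at N=24, and ANCOVA is slightly worse at N=16. With follow-up SD 1.2 times baseline SD, the gain is about 1% or less from r=0.7 upwards. Under 3:1 allocation the pooled slope is dominated by the SB623 arm, so additive ANCOVA can lose precision even at N=52. All of this stands, and it is why the adjusted model belongs beside the planned tests and not in their place.

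A reader might infer that these two appendices break an otherwise uniform rule of baseline adjustment. The documents do not support that. Laboratory and vital-sign changes are also compared unadjusted, and the Appendix F statement is an explicit choice. The contrast is only with the efficacy scales and the Fugl-Meyer analyses.

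A reader might also infer bias or an inflated error rate. Under randomisation the unadjusted t-test on change is valid; chance imbalance is part of its sampling error.

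The objection does not remove two facts: the baseline is already in the dataset, and with about 13 or fewer sham patients a sizeable imbalance is an ordinary event that the planned tables cannot correct.

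**Conclusion.** The point holds as a low-priority improvement. For continuous leg-activity and head-MRI variables, the plan makes no use of a collected baseline beyond subtracting it. The expected benefit is a variance lower by about 3% to 23% at N=52 and 1% to 22% at an assumed N=30, over r from 0.9 to 0.5, together with protection against a 0.5 SD imbalance that arises in about 12% of randomisations at 39:13. These figures rest on equal variances, equal baseline slopes, and correlations and leg-activity sizes that the documents do not give. If r is high, the gain is close to nothing. If sham follow-up tracks baseline much more closely than SB623, variance can be about 5% higher even at N=52.

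A firm claim that ANCOVA must be more precise here, or that the larger gains are the expected ones, would go beyond what the documents allow. The primary result, its sample size and its error rate are unaffected.

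**What to change.** In SAP Appendix F, 7.0 and Appendix E, 7.2, keep the planned tests and add beside them:

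- ANCOVA on change at each visit, with treatment and that variable's own baseline, reporting the adjusted difference and 95% CI.
- The same baseline term in the dose regressions, keeping each appendix's dose set (control at dose 0 in Appendix E, control excluded in Appendix F).

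Apply this to continuous variables that have a baseline value, in the overall sets and in the lower extremity deficit set, since the latter is the protocol's leg-activity endpoint. Do not extend it to the Day 8 lesion subsets: Appendix E, 5.6 recognises that they are defined after treatment, and a baseline covariate would not restore comparability there. Leave the one-sample summaries and the Day 8 lesion descriptives as they are.

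The addendum to the main SAP (section 3.0) records that interim results have been unblinded. Wherever the plan can no longer be changed, label the ANCOVA as a sensitivity analysis added after that unblinding.

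The cost is SAP wording and programming, with no new data, and one degree of freedom per model: in variance, about 2% at N=52 (49/48), 4% at N=30 (27/26), 5% at N=24 (21/20) and 8% at N=16 (13/12). Precision may be slightly lower than that of the t-test when N is small and r high, or when the arms' baseline slopes differ as shown above. Reporting both analyses makes that visible.
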